### **3.2 Secondary objectives**

- To measure the acceptability of, uptake and adherence to the range of behavioural and biomedical prevention options, including pre-exposure prophylaxis (when available).
- To measure HIV and other sexually transmitted infection incidence rates.
- To assess trends in sexual behaviour.
- To measure pregnancy rates.

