### **3.3 Study overview**

This is a prospective observational cohort study.

Up to 2,500 sexually active, HIV-uninfected women between the ages of 18 and 30 years will be enrolled from an urban, a peri-urban and a rural site in KwaZulu-Natal, South Africa. Potential study participants will be screened for eligibility and eligible participants will be enrolled in the study within 30 days of screening. Participants will have monthly visits for the first three months post-enrollment, thereafter visits will be scheduled every three months.

HIV and pregnancy testing will be performed at each study visit and the incidence of pregnancy, as well as HIV and other STIs will be assessed. HIV/STI risk reduction messages and HIV prevention methods (e.g. condoms) will be offered to all participants using consistent prevention messages. It is anticipated that PrEP use will increase during this study. Uptake and adherence to PrEP and other HIV prevention modalities will be assessed during follow up. A HIV risk perception and behavioural assessment using an interviewer administered questionnaire will be conducted at each visit. In addition, an acceptability assessment of expanded HIV prevention options (oral tablets, rings, injectables and implants) will be conducted through an interviewer administered questionnaire at enrolment and study exit. Blood and genital specimens will be collected and stored every three months and will be used for potential post-study assessments for markers of safety, risk exposure, PrEP adherence and resistance. In addition, stored plasma will be used for retrospective RNA PCR testing to confirm whether incident cases of early HIV infection during the study occurred post-enrolment.

An open cohort will be maintained for up to 5 years. Participants may be simultaneously enrolled in or may transition to other studies as appropriate.

Overviews of the study visit and procedures schedules are presented in Appendix I: Schedule of Evaluations.

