## **5.4 Follow-up visits**

Monthly follow-up visits are scheduled on a 28-day schedule for the first three months, with a 14-day visit window on either side. Thereafter visits will be scheduled on an 84-day schedule (every three months), with a 28-day visit window on either side. For participants who do not complete scheduled visits within the allowable window, the visit will be considered “missed” and relevant CRFs will be completed to document the missed visit.

HIV-uninfected study participants who become infected during follow-up will be referred to one of the long-term CAPRISA Acute Infection cohort studies, which have provisions for care, ART and support for those infected with HIV. These services are provided at no cost to the participant. For those who do not wish to continue in any of these studies post-seroconversion, participants will be referred to their preferred AIDS care provider which could include government or non-governmental AIDS care services for ongoing clinical management and care.

Participants who become pregnant during follow-up may be maintained in this study, however follow-up procedures may be modified according to guidelines specified in the study-SOPs, i.e. the principal change will be the discontinuation of pelvic examinations and genital specimen collection after 24 weeks of pregnancy.

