### **5.4.2 Clinical procedures**

- Medical history
- Targeted physical examination
- Blood draw (at quarterly follow-up visits only or if indicated, e.g. at the time of suspected HIV seroconversion)
- Provision of test results
- Pelvic examination (at quarterly follow-up visits only or if indicated, e.g. at the time of suspected HIV seroconversion)
- Genital specimen collection (at quarterly follow-up visits only or if indicated, e.g. at the time of suspected HIV seroconversion)

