#### **6.2.2 Secondary analysis**

Acceptability of HIV prevention options will be measured using acceptability questionnaires administered during interviews with the participants. These interviews will include questions about the uptake of different prevention options. Prevention choices will be described by giving the number and percentage of participants who prefer various prevention options at different time points. The acceptability and uptake of the HIV prevention options will be summarised at different time points. The acceptability and uptake in different age groups will be compared using Fisher's exact test.

Adherence to prevention options will be measured as appropriate according to the prevention method; for example oral tablets will be measured using pill counts and drug level data. Adherence will be summarised at various time points, by giving the percentage adherence. For pill counts adherence will be calculated as the number of pills taken according to pill count (number dispensed minus number returned) divided by the number of pills prescribed in the time period. Adherence for other options may be defined as a binary variable: adherent, not adherent – based on some predefined criteria. The proportion adherent participants will then be summarised at various time points.

STIs will be measured using laboratory assessments of urine, plasma and/or genital specimens. The incidence rate of the various STIs (including HIV) will be calculated as the number of new infections over the time on study. A Poisson distribution will be assumed for the confidence intervals of incidence rates.

Sexual behaviour will be ascertained through interviews with the enrolled participants where questions about sexual behaviour related to HIV risk (e.g. number of partners, condom use and use of HIV prevention interventions, etc.) will be asked. Trends in sexual behaviour will be summarised over time using means and proportions at the various time points. If needed longitudinal mixed models will be fit to determine whether there are changes over time.

Pregnancy will be defined as a positive pregnancy test. The pregnancy incidence rate will be calculated as the number of new infections over the time on study. A Poisson distribution will be assumed for the confidence intervals of incidence rates.

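### Pregnancy is defined as a positive test, but scheduled tests are 84 days apart after month 3, so short pregnancies can be missed and the secondary pregnancy rate modestly understated

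*Protocol*

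**What the plan says.** Section 3.2 lists among the secondary objectives: "To measure pregnancy rates". Section 6.2.2 gives the case definition: "Pregnancy will be defined as a positive pregnancy test". It names no other source of events.

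Section 3.3 and Appendix I place a pregnancy test at every study visit. Section 5.4 sets the spacing. Early on, "Monthly follow-up visits are scheduled on a 28-day schedule for the first three months, with a 14-day visit window on either side". After that, "Thereafter visits will be scheduled on an 84-day schedule (every three months), with a 28-day visit window on either side". Section 3.3 adds: "An open cohort will be maintained for up to 5 years".

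Two other routes by which a pregnancy could come to light are open. "Medical history" is a listed clinical procedure at follow-up (section 5.4.2), and Appendix I schedules it at every visit. Section 5.6 allows interim visits at any time, with an open list of reasons. Neither is tied to the pregnancy endpoint.

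**The concern.** HIV infection persists, so a later test still finds it. Pregnancy does not persist: one that begins and ends between two tests leaves no positive test at a visit. A definition built on a positive test therefore depends on how often tests are done, and here the scheduled gap triples after month 3.

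The stake is a stated secondary objective. Events missed from the numerator, with follow-up time unchanged, bias the rate downwards. The bias is larger in the quarterly phase, which makes up most of the follow-up of any woman who stays a year or more.

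A separate wording slip sits in the same section: "The pregnancy incidence rate will be calculated as the number of new infections over the time on study". Replacing infections with pregnancies there would leave the present point untouched.

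**Working it through.** The protocol states no expected pregnancy rate, precision or power for this objective, so there is no figure to reproduce.

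**Inputs from the protocol**
- Gap between tests: T = 28 days to month 3, then T = 84 days (section 5.4).
- Widest gap between consecutive quarterly visits inside their windows: 84 + 28 + 28 = 140 days.
- Nominal gap after one missed quarterly visit: 2 x 84 = 168 days.

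**Inputs assumed, because the protocol gives neither**
- Share s of pregnancies that end early: 10-25%.
- Days D for which such a pregnancy would test positive: 14 to 70 days (2-10 weeks).

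**Step 1: chance of a miss.** With onset uniform over the gap, P(missed) = max(0, 1 - D/T).

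| D (days) | T = 28 | T = 84 | T = 140 |
|---|---|---|---|
| 14 | 50% | 83% | 90% |
| 28 | 0% | 67% | 80% |
| 42 | 0% | 50% | 70% |
| 56 | 0% | 33% | 60% |
| 70 | 0% | 17% | 50% |
| 84 | 0% | 0% | 40% |

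At nominal quarterly spacing, a pregnancy testable for 84 days or more is always caught.

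**Step 2: effect of the visit windows.** Simulating visit dates uniformly within the windows gives, quarterly against monthly:
- D = 28: 67% against 17%
- D = 42: 50% against 2%
- D = 56: 35% against 0%

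The windows hardly change the quarterly result. They let some short pregnancies through in the monthly phase.

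**Step 3: undercount as a share of all pregnancies, s x P(missed), at nominal spacing.**
- Quarterly, D uniform on 14-70 days: mean D = 42, so mean P(missed) = 1 - 42/84 = 50%. The undercount is 0.10 x 50% = 5% to 0.25 x 50% = 12.5%.
- Quarterly, single values of D at the extremes: 0.10 x (1 - 70/84) = 1.7% to 0.25 x (1 - 14/84) = 20.8%.
- Monthly, D uniform on 14-70 days: only D below 28 can be missed. That is 14/56 = 25% of the range, with an average miss of 25% (falling linearly from 50% to 0), so mean P(missed) = 6.25%. The undercount is 0.10 x 6.25% = 0.6% to 0.25 x 6.25% = 1.6%.

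**Step 4: weight of the quarterly phase.** Three 28-day intervals take 84 days. The share of follow-up after that is 1 - 84/365 = 77% for one year, 1 - 84/730 = 88% for two years and 1 - 84/1826 = 95% for five years. An overall rate therefore carries most of the quarterly undercount.

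**The case against.** The strongest reply is that section 6.2.2 is being read too narrowly. A reader might infer that only a test at a study visit counts, but the text says neither. A positive test at an interim visit fits the definition (section 5.6), and so could a documented positive test done elsewhere, since section 6.3 provides for CRF data taken from external records. This stands, and it means that the figures above describe scheduled testing alone; interim and outside tests would reduce them. It does not rescue a loss, termination or delivery reported without a test, which falls outside the definition as worded.

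A second reply is that source rules for events belong in the statistical analysis plan, which is not shown. That would be decisive if the protocol had left the definition open. It states one, so a plan that counted reported losses would be widening it.

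A reader might also infer that pregnancies between visits are never counted. The formula does not support that: at 84 days, those testable for 8 or 10 weeks are caught 67% or 83% of the time, and continuing pregnancies are found later. Losing a full-term pregnancy would take several consecutive missed visits, an edge case against the 90% annual retention target in section 4.5.

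Finally, a test-based definition is objective and uniform across three sites, whereas self-report is not verified. That is a fair reason to keep the test-confirmed rate in view.

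**Conclusion.** The point holds as a minor one. With events taken from scheduled tests, the pregnancy rate is understated, and more so after month 3. The direction follows from the definition and the schedule. The size rests on two assumptions that the protocol cannot supply: with 10-25% of pregnancies ending early and testable length uniform on 2-10 weeks, the undercount is about 5-12.5% in the quarterly phase (1.7-20.8% across single values) and about 0.6-1.6% in the monthly phase, at nominal spacing.

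A reader might go further and expect a spurious downward trend in the results. The protocol plans no trend analysis for pregnancy; trends are an objective for sexual behaviour only. What can be said is conditional: pregnancy rates broken down by time on study, if reported, would partly reflect test spacing. The primary analysis of risk factors for HIV acquisition is unaffected.

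**What to change.** In section 6.2.2, define an incident pregnancy as either a positive pregnancy test (scheduled, interim or documented elsewhere) or a pregnancy since the last visit recorded in the medical history, including one that ended in loss, termination or delivery. Count each pregnancy once. Report the test-confirmed rate alongside.

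The cost is one or two sentences in 6.2.2 and, if the CRFs do not already carry it, one medical-history item per visit. No extra visit or test is needed. The downside is that some added events rest on self-report; the gap between the two rates shows how many.

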### 4.1 Inclusion criteria

Women must meet all of the following criteria at enrolment (by self-report, unless otherwise indicated) in order to be eligible for inclusion in the study:

- Female
- Age 18-30 years (inclusive)
- Able and willing to provide written informed consent to be screened for, and to enrol in, the study
- Able and willing to provide adequate locator information for study retention purposes
- Sexually active (sexual intercourse at least three times in the last 3 months)
- HIV negative on testing performed by study staff
- Have a negative pregnancy test performed by study staff
- Agree to adhere to study visits and procedures

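### The pregnancy incidence formula counts infections instead of pregnancies and divides by follow-up time that includes time already pregnant

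*Protocol*

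**What the plan says.** Section 3.2 lists among the secondary objectives: "To measure pregnancy rates". Section 6.2.2 gives the only estimator for it, in three sentences. The event: "Pregnancy will be defined as a positive pregnancy test". The rate: "The pregnancy incidence rate will be calculated as the number of new infections over the time on study". The interval: "A Poisson distribution will be assumed for the confidence intervals of incidence rates".

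Earlier in the same section, the STI and HIV rate has the same form: "The incidence rate of the various STIs (including HIV) will be calculated as the number of new infections over the time on study".

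Three other provisions bear on the calculation:
- Entry (section 4.1) requires each woman to "Have a negative pregnancy test performed by study staff", so nobody starts follow-up pregnant.
- Testing (section 3.3) is frequent: "HIV and pregnancy testing will be performed at each study visit". Appendix I shows the urine pregnancy test at every visit.
- Retention (section 5.4): "Participants who become pregnant during follow-up may be maintained in this study". The principal change named for these women is that pelvic examinations and genital specimens stop after 24 weeks, so follow-up into late pregnancy is foreseen.

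**The concern.** Read as written, the formula does not give a pregnancy rate, because infections are not pregnancies. The protocol does not leave this open for a later document. It states a formula, and an analysis plan with the right one would depart from the protocol.

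Correcting the event does not settle the denominator. A woman who is already pregnant is not at risk of a new pregnancy, yet her time keeps accruing. The result is a rate that is too low, by more where pregnancy is more frequent. What is at stake is the accuracy of one descriptive secondary result, and whether it can be compared with rates calculated on time at risk.

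**Working it through.** **1. Numerator.** No arithmetic is needed. Section 6.2.2 uses the same numerator and denominator for STIs (including HIV) and for pregnancy. The first use is coherent. The second names a different event from the one that the pregnancy paragraph has just defined.

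**2. Denominator: why the phrase works for HIV and not for pregnancy.**

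| | HIV | Pregnancy |
|---|---|---|
| After the event | Confirmed seroconverters are scheduled for exit (7.5.2) | Woman may stay in follow-up (5.4) |
| Event and censoring dates | Midpoint of last negative and first confirmed positive test; last negative test if uninfected (6.2.1) | None stated |
| Can the event recur? | No | Yes, in an open cohort of up to 5 years (3.3) |

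For HIV, time on study is close to time at risk. For pregnancy it is not.

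**3. Size of the denominator effect.** The protocol gives no pregnancy rate, expected count or precision, so there is no figure of its own to reproduce. The following is illustrative.

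Assumptions, none from the protocol: constant true rate *r* of 3, 6, 10 or 15 per 100 woman-years; each pregnancy lasts 266 days (*d* = 266/365.25 = 0.728 years) and is followed to its end or to the end of follow-up; no dropout; risk resumes when the pregnancy ends; 1 to 5 years of follow-up.

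The simulation used 20,000 women per scenario. The number of pregnancies was divided once by time at risk and once by total time.

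| Assumed rate per 100 woman-years | 1 year: at-risk → total time | Change | 5 years: at-risk → total time | Change |
|---|---|---|---|---|
| 3 | 2.94 → 2.90 | -1.4% | 2.99 → 2.94 | -1.7% |
| 6 | 6.25 → 6.08 | -2.7% | 5.99 → 5.76 | -3.8% |
| 10 | 10.09 → 9.63 | -4.6% | 10.08 → 9.44 | -6.3% |
| 15 | 15.30 → 14.26 | -6.8% | 15.07 → 13.68 | -9.2% |

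**4. Check by formula.** The ratio of the two rates equals the expected share of follow-up spent at risk.
- One year, *r* = 0.10. Time before a first pregnancy: (1 - e^(-0.10))/0.10 = 0.9516. Time at risk again after a pregnancy that ends within the year: about *r*(1 - *d*)²/2 = 0.10 × 0.0738/2 = 0.0037. Sum 0.9553, a bias of -4.5%; the simulation gives -4.6%.
- Long-run limit: 1/(1 + *rd*). At *r* = 0.10 this is 1/1.0728 = 0.932, or -6.8%. At *r* = 0.15 it is 1/1.1092 = 0.902, or -9.8%. The five-year results (-6.3% and -9.2%) approach these limits without reaching them, as they should.

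**The case against.** The strongest reply is that the numerator is a slip of the pen. The paragraph opens by defining pregnancy and names the quantity a pregnancy rate, so no analyst would put infections on top. As a forecast of what will be done, that is probably right. It does not make the sentence correct, and this is the only formula the protocol gives for the objective.

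Second, the person-time convention is a detail that an analysis plan, not shown here, normally settles, and the bias is small. Early losses, terminations and dropout would shorten the pregnant time in follow-up and shrink the bias further. All of this stands and limits the weight of the point. The denominator is nevertheless named in the protocol, and time on study is not time at risk.

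Two stronger readings are tempting, and the document supports neither.
- A reader might infer that every positive test counts as a pregnancy, so that a full-length pregnancy on the 84-day schedule is counted about three times. The text does not prescribe this. The definition says how a pregnancy is ascertained, and the formula counts new events. What is missing is only an explicit rule for telling one pregnancy from the next.
- A reader might infer that the bias distorts comparisons by age, site or contraceptive method. No such comparison of pregnancy rates is planned. The Fisher's exact test by age group in section 6.2.2 concerns acceptability and uptake, and section 6.1 speaks of comparing risk factors for HIV.

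**Conclusion.** The formula is wrong as written. The numerator error is certain and rests on no assumption. The denominator error is real but modest: a downward bias of about 1-2% at 3, 3-4% at 6, 5-6% at 10 and 7-9% at 15 per 100 woman-years. These sizes depend on assumed rates, full-length pregnancies and complete follow-up, so they lean towards the upper side for each assumed rate.

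The severity is minor to moderate. One descriptive secondary objective is affected. The proportional hazards analysis in section 6.2.1 and the sample size in section 6.1 are not, and the correct rate can be computed from data the study plans to collect.

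**What to change.** Replace the rate sentence in the pregnancy paragraph of section 6.2.2 with wording such as:

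*The pregnancy incidence rate is the number of new pregnancies (first positive test of each pregnancy, after a negative test) divided by woman-years at risk of pregnancy. Time at risk runs from enrolment to the estimated onset of pregnancy, taken as the midpoint between the last negative and first positive test, or to the last negative test for women who do not become pregnant.*

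Then choose one rule for later pregnancies and state it: either time at risk restarts at the first negative test after a pregnancy, or follow-up for this outcome is censored at the first pregnancy.

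The midpoint matters. Ending the time at risk of women who conceive at their last negative test would discard time before conception and push the rate upward. Both the midpoint and the restart at a negative test use visit-level results only, so no separate conception or delivery date is needed.

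The cost is one rewritten paragraph. No new visits, tests or forms follow from it, and the Poisson interval can stay.

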### **6.3 Data management**

Data will be collected on data collection forms (CRFs), which will be developed by the study team. All research clinic study staff will be trained in the correct completion of CRFs. If data entered on the CRFs are taken from an external source (e.g., laboratory reports, patient records), the source documents will be maintained in the participant's study file at the research clinic, and will be available for review. The data will

be entered into the database management system which is DataFAX running on a four node Dell R730 Virtual SAN Cluster within a SUSE Linux operating system environment on a VMWare Enterprise Virtualised Platform.

Queries arising during validation of the data will be recorded in quality control (QC) reports sent to the research clinics on a regular basis. Any queries resulting in a change to the database will be documented and attached to the original CRF. The data management centre staff will perform periodic QC and validation checks on the data. Database files will be password-protected and access to the files will be limited to authorised study staff members only. All data will be backed up at regular intervals, and backups will be stored in secure areas with limited access.

All documents will be stored securely at the research clinics and both during and after the completion of the study. At all research clinics the forms will be stored in locked cupboards in a secure room with restricted access. Upon completion of the study, the close-out research clinic monitoring visit and finalisation of the database for analysis, the original forms will be bound and kept for long term storage.

## **7 HUMAN SUBJECTS CONSIDERATIONS**

### **7.1 Regulatory and ethical review**

This study will be conducted under the oversight of the UKZN's BREC in accordance with International Conference on Harmonization (ICH) standards of Good Clinical Practice (GCP). CAPRISA will be responsible for reporting study-related information to the UKZN BREC. The study will only be initiated after it has been approved by the UKZN BREC. The study will be conducted in accordance with all conditions of approval by the ethics committee.

